## 1.0 TRIAL SUMMARY

Abbreviated Title	Focused Ultrasound combined with Pembrolizumab in Metastatic Breast Cancer
Trial Phase	Pilot
Clinical Indication	Metastatic Breast Cancer
Trial Type	Investigator Initiated
Type of control	N/A
Route of administration	IV
Trial Blinding	N/A
Treatment Groups	Arm A: Pembrolizumab after High-Intensity Focused Ultrasound (HIFU) Arm B: Pembrolizumab before High-Intensity Focused Ultrasound (HIFU)
Number of trial subjects	Up to 15
Estimated enrollment period	2 years
Estimated duration of trial	3 years
Duration of Participation	90 days to 2 years
Estimated average length of treatment per patient	90 days

## 2.0 TRIAL DESIGN

### 2.1 Trial Design

This is a two-arm pilot study of High-Intensity Focused Ultrasound (HIFU) and immunotherapy. The goals of the study are to obtain preliminary data on the safety of HIFU with immunotherapy, delivered concurrently, and to obtain preliminary estimates of change in T-cell frequency and activation for HIFU alone (day 15-21 of ARM A) and pembrolizumab and HIFU given in combination (day 15-21 of arm B). The central hypothesis is that focused energy induced immunogenic cell death will overcome limitations in antigen availability, and effective T-cell responses, and thereby enhance immune-therapy of advanced breast cancer. Our secondary hypothesis is that concomitant immune-activation will further augment CD8+ T-cell responses to tumor antigen released by HIFU. We will obtain preliminary data on whether HIFU promotes the presence of CD8+ T-cells in ablated primary tumors, blood and non-ablated distant metastases. Additional correlative science endpoints will be tested as exploratory endpoints.

[figure not shown]
Eligible subjects will be randomized 1:1 to the investigational treatments (Arm A) or (Arm B). Subjects on both arms will undergo HIFU treatment on day 15. Subjects randomized to Arm A will receive pembrolizumab administered IV every 3 weeks on days 22, 43, and 64. Subjects randomized to Arm B will receive pembrolizumab administered IV every 3 weeks on days 1, 22, 43 and 64. In all subjects, restaging breast cancer-dedicated chest, abdomen and pelvic CT scan will be performed at baseline and cycle 4. Biopsies of tumors treated with HIFU will be completed on all patients at days 1 and 22 with optional distant tumor site biopsies and additional biopsies of the HIFU treated breast lesion to be completed at day 64. The tissue removed at the biopsies will be evaluated as part of the immunologic correlative studies.

**Product:** Pembrolizumab

**Protocol/Amendment No.:** UVA Breast 48

V04-13-21

## 2.2 Trial Diagram

\* Biopsies of HIFU treated lesion and distant tumor site are optional at cycle 4  
Biopsies offset from HIFU to avoid air bubbles within US path.  
There is an option to continue Pembrolizumab if response observed.

## 3.0 OBJECTIVES & HYPOTHESES

### 3.1 Primary Objectives & Hypotheses

**Objective:** To determine whether the addition of pembrolizumab to HIFU increases the proportion of CD8+ tumor infiltrating lymphocytes (ratio CD8+/CD4+) in the primary ablation zone of advanced or metastatic breast cancer.

**Hypothesis:** Focused energy induced immunogenic cell death is hypothesized to improve antigen availability, dendritic cell activity, effective T-cell responses. In combination with pembrolizumab, it is hypothesized that CD8+/CD4+ ratio in the ablation zone will increase by 25%.

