### 3.3 Exploratory Objectives

- (1) **Objective:** To compare CD8+ T-cell responses at peri-ablation zones when pembrolizumab is given before or after HIFU. (CD8+/CD4+ ratios compared between arms)
- (2) **Objective:** To evaluate clinical responses at local and distant metastatic sites by CT scan as measured by RECIST 1.1.
- (3) **Objective:** To estimate the progression free survival (PFS) of breast cancer subjects treated with HIFU in combination with pembrolizumab.
- (4) **Objective:** To estimate the overall survival (OS) of subjects with breast cancer treated with HIFU in combination with pembrolizumab.
- (5) **Objective:** To evaluate immune responses to HIFU plus pembrolizumab by flow cytometric, immunohistochemical, cytokine, or other methods.

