#### **4.4 Rationale for Endpoints**

This study is designed primarily to test whether interfering with immune suppression by blocking the molecular interaction between the PD-1 receptor and its cognate ligand, PD-L1, increases the number and activation of TILs that are induced by the local ablative therapy.

The study is also designed to examine the safety of HIFU and pembrolizumab. HIFU therapy for breast lesions and breast cancer is generally well tolerated. Based on our experience at UVA (n=20) there has been no evidence of grade 4 toxicities in patients who received HIFU. Pembrolizumab has been studied in numerous clinical trials to date and was found to be well tolerated with no dose-limiting toxicities at the standard dose of 200 mg (see Investigator's Brochure). Our proposed study is the first study to combine HIFU and pembrolizumab in humans and safety is our secondary endpoint.

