## **8.0 STATISTICAL ANALYSIS PLAN**

### **8.1 Statistical Analysis Plan Summary**

This is a pilot study of high intensity focused ultrasound (HIFU) and pembrolizumab, and is proposed as a pilot two-arm design. All patients will receive the FDA approved dosing of pembrolizumab and allocation to arms is randomized. Participants from arm A will first receive HIFU ablation and then a pembrolizumab infusion 1 week after an ablative procedure. Participants from arm B will first receive pembrolizumab at baseline and then undergo the HIFU ablation two weeks later. The goal is to obtain preliminary data on the safety of HIFU and pembrolizumab and to obtain estimates of change in immune parameters (proportion of activated CD8 tumor infiltrating lymphocytes (TILs) is primary) pre- and post-treatment. The trial will not be powered for cross arm comparison, but will nevertheless provide useful pilot data for the design of a larger trial of combined therapies.

Safety stopping rules will be employed within each study arm and will be judged by dose limiting toxicities (DLTs), defined in [Section 7.2.10](#). The primary objectives include assessing adverse events

**Product:** Pembrolizumab

**Protocol/Amendment No.:** UVA Breast 48

V04-13-21

and change in the proportion of CD8+ to CD4+ tumor infiltrating lymphocytes (TILs) in the primary ablation zone. Secondary endpoints include assessing change in CD8+ T-cell responses at peri-ablation zones, clinical responses at local and distant metastatic sites, disease free survival (DFS), and overall survival (OS). Exploratory endpoints include assessing change in T-cells in peripheral blood, markers of T-cell activation, gene expression profiling, and enumeration of myeloid derived suppressor cells.

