## 8.2 Statistical Analysis Plan

Target sample size is 12 participants, which was chosen as a feasible number that could be accrued within a 2 year accrual period. Participants will be randomized 1:1 to treatment arms A and B with block randomization using blocks of size 2 or 4. Participants are considered evaluable if they satisfy all inclusion and exclusion criteria and have adequate endpoint measurements during respective cohort timelines. Adjusting for a 10% unevaluable/drop-out rate, maximum target accrual is estimated at 15 participants.

The purpose is to assess the adverse events profile of pembrolizumab and focused ultrasound therapy and estimate the difference in the TILs at baseline and 3 weeks within each arm, not to make definitive comparisons between arms. With 6 participants per arm, there is limited power to make comparisons between arms. Lu et. al. (2009) data estimates the difference in means of the ratio of CD4+ and CD8+ cells for patients treated with HIFU versus no HIFU to be 0.57, with standard deviations ranging from 0.27 to 0.40. These data provide an indication of the magnitude that could be detected in this study at baseline and 3 weeks, where it is assumed that the no HIFU participants in Lu et. al. are comparable to baseline measurements in our study. Using these data as a guideline, with n=6, we have 80% power to detect an effect size of 1.44 for the within-arm change in ratio of CD4+ and CD8+ cells at baseline and 3 weeks. Depending on the variability of the data, this is equivalent to detecting differences of 0.39 and 0.58, for assumed standard deviations of 0.27 and 0.40, respectively. The populations will include all intention to treat participants.

Safety stopping rules will be employed within each arm and will be judged by dose limiting toxicities (DLT). If the first two participants within an arm or 3 out of the 6 participants within an arm experience a DLT, that arm will be deemed too toxic and further accrual to that arm will be closed. This decision rule is based on Wald's sequential probability ratio test assuming lower and upper DLT proportions of 0.1 and 0.3, respectively, and type I and II error rates of 10%.

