Adverse events and DLTs will be summarized by frequency and magnitude for each arm and overall. Change in the proportion of CD8+ to CD4+ tumor infiltrating lymphocytes (TILs) in the primary ablation zone will be estimated by arm. Additionally change in CD8+ T-cell responses at peri-ablation zones and clinical response at local and distant metastatic sites measured by abscopal tumor shrinkage at non-ablated sites, will be estimated for each arm. The Kaplan Meier estimator will be used to estimate survival curves for DFS and OS. Exploratory endpoints including change in T-cells in peripheral blood, markers of T-cell activation, gene expression profiling, and enumeration of myeloid derived suppressor cells will be estimated by arm.

If highly favorable responses are seen in this pilot patient population, then this study may be expanded by means of an amendment to more rigorously define response criteria in either or both arms.

**Product:** Pembrolizumab

**Protocol/Amendment No.:** UVA Breast 48

V04-13-21

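### The primary objective asks what pembrolizumab adds to HIFU, but the planned primary analysis is within-arm change, which cannot separate the two

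*Combined protocol and SAP*

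**What the plan says.** **The question.** Section 3.1 states the primary objective as "To determine whether the addition of pembrolizumab to HIFU increases the proportion of" CD8+ infiltrating lymphocytes, expressed as CD8+/CD4+, in the primary ablation zone. Section 4.4 gives the same reading: the main purpose is to test whether PD-1 blockade "increases the number and activation of TILs that are induced by the local ablative therapy". Both describe an increment over HIFU.

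**The exposure at the biopsy.** Section 2.1 randomises 1:1, gives HIFU on Day 15 in both arms, and requires biopsies on Days 1 and 22. It describes the two states being measured as "HIFU alone (day 15-21 of ARM A) and pembrolizumab and HIFU given in combination (day 15-21 of arm B"). Section 5.2.3 places dosing after the visit's procedures, so Arm A's Day 22 biopsy comes before its first pembrolizumab infusion.

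**The analysis.** Section 8.2 says the purpose is to "estimate the difference in the TILs at baseline and 3 weeks within each arm, not to make definitive comparisons between arms". Its power statement reads "we have 80% power to detect an effect size of 1.44 for the within-arm change in ratio of" CD4+ and CD8+ cells, with 6 participants per arm. For the primary endpoint, the change in CD8+ to CD4+ "tumor infiltrating lymphocytes (TILs) in the primary ablation zone will be estimated by arm". Section 8.1 adds: "The trial will not be powered for cross arm comparison".

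**Between-arm comparisons elsewhere.** Exploratory objective 1 in Section 3.3 has "ratios compared between arms", but for the peri-ablation zone. Section 4.4.1 speaks of estimating a difference between the two treatment groups in tissue biomarkers after treatment. Section 8 carries forward no such difference for the primary endpoint.

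**The concern.** The objective and the analysis concern different quantities. The objective concerns the effect of pembrolizumab given HIFU. The analysis produces a before-and-after change in each arm. In Arm A that change reflects HIFU plus time and the earlier biopsy. In Arm B it reflects the same things plus pembrolizumab. Neither one isolates pembrolizumab.

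The plan itself expects HIFU to move the ratio, because Section 8.2 bases its sizing on a HIFU versus no-HIFU difference of 0.57. A rise in Arm B is therefore expected even if pembrolizumab is inert in the ablation zone, and it could be reported as support for the primary hypothesis. Conversely, if HIFU moved the ratio the other way, a flat result in Arm B could hide a real pembrolizumab effect. The second possibility cannot be ruled out from the text: Section 3.1 uses CD8+/CD4+, whereas Section 8.2 quotes 0.57 for a ratio of CD4+ and CD8+ cells, so its direction for CD8+/CD4+ is unclear.

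**Working it through.** The mismatch follows from the text. The arithmetic shows what kind of test the plan sized and how far within-arm change could mislead.

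**Inputs (Section 8.2).** n = 6 per arm; effect size 1.44 at 80% power; HIFU versus no-HIFU difference 0.57; SDs 0.27 and 0.40. Alpha is not stated for this calculation; two-sided 0.05 is inferred because it reproduces the plan's figure. No test is named; a paired test is implied by the power statement.

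**1. Reproduce the plan's figure.** Paired t-test, noncentral t with 5 df and noncentrality d × √6. At d = 1.44, power = 80.3%; exactly 80% needs d = 1.43. Also 1.44 × 0.27 = 0.39 and 1.44 × 0.40 = 0.58, as stated. A two-sample t-test with 6 per arm would need d = 1.80 for 80% power, and has 61% power at 1.44. The plan's figure is therefore a within-arm calculation.

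**2. HIFU works, pembrolizumab adds nothing.** Arm B's true change is then 0.57.

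| Basis for the SD of change | SD of change | Chance Arm B's paired test is significant |
|---|---|---|
| Plan's SDs are SDs of change | 0.27 / 0.40 | 98% / 79% |
| Single-timepoint SDs, correlation 0 | 0.382 / 0.566 | 83% / 51% |
| Single-timepoint SDs, correlation 0.75 | 0.191 / 0.283 | over 99% / 97% |

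Rows 2 and 3 use SD of change = SD × √(2(1 − ρ)); ρ is the assumed correlation between the Day 1 and Day 22 values. At ρ = 0.5 the result equals row 1. The lower rows are needed because Section 8.2 does not call 0.27 and 0.40 SDs of change.

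**3. The opposite case (assumed effects, not from the documents).** HIFU shifts the ratio by −0.57 and pembrolizumab by +0.57. Arm B's mean change is −0.57 + 0.57 = 0, so its paired test is significant only 5% of the time. The Arm B minus Arm A difference is 0.57, which a two-sample t-test with 6 per arm detects 91% (SD of change 0.27) or 61% (0.40) of the time. With single-timepoint SDs these become 65% / 35% at ρ = 0 and over 99% / 88% at ρ = 0.75.

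**4. Precision of the difference that matches the objective.** The 95% half-width is 2.228 × √(2/6) × SD of change (10 df, raw scale, unadjusted):
- SDs of change: 2.228 × 0.577 × 0.27 = 0.35, and × 0.40 = 0.51.
- Single-timepoint SDs: 0.49 / 0.73 at ρ = 0; 0.25 / 0.36 at ρ = 0.75.

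The difference detectable with 80% power is 1.80 SD of change: 0.48 to 0.72 on the plan's SDs as SDs of change, and 0.34 to 1.02 over ρ from 0 to 0.75.

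**The case against.** The strongest reply is that this is a 12-patient pilot that openly declines cross-arm inference. Sections 2.1, 8.1 and 8.2 agree that the aim is per-arm estimates of change. On that view Section 3.1, with its echo in Section 4.4, is simply out of line, and its 25% hypothesis names no comparator and could be read as Arm B's own change. Both arms are biopsied on Days 1 and 22 and both changes will be reported, so anyone can subtract. Section 4.4.1 shows that a two-group difference was intended, and CD4/CD8 infiltrating cells are the first biomarker listed under it.

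Much of this is fair. Nothing is lost from the design or the data, and rewording Section 3.1 would be enough to remove the conflict. Making an unpowered contrast primary would depart from a deliberate choice. The rejection rates also presume a test that Section 8.2 only implies, and the cancelling case in step 3 was constructed to show the mechanism.

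It does not remove the point. Lack of power makes an interval wide; it does not turn within-arm change into an estimate of pembrolizumab's added effect. Declining a definitive comparison is different from planning an estimated one, and Section 3.1 still promises a determination. If readers subtract the arm estimates themselves, the answer to the primary question becomes an unplanned calculation with no planned interval. Section 4.4.1 makes the documents inconsistent, because Section 8 does not take up what it announces.

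**Conclusion.** The concern holds. As written, the primary objective in Section 3.1 has no planned analysis that estimates the effect it names, and this must be corrected. The randomised Day 22 contrast could supply the estimate, so the fault lies in the objective wording and the analysis plan, not in the arms or the biopsies.

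Confidence is high for the mismatch, which needs no assumption about effect sizes. The size of the possible error is illustrative. With no pembrolizumab effect and a HIFU shift of 0.57, Arm B's change would be significant 79% to 98% of the time on the plan's SDs as SDs of change, or 51% to over 99% if they are single-timepoint SDs with correlation 0 to 0.75. These figures rest on a paired t-test at an inferred two-sided 0.05 and on the 0.57 applying to the ratio analysed.

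**What to change.** Do one of the following.

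**(a) Keep the question and add its estimate.** In Sections 3.1 and 8.2, name the primary estimate as the Arm B minus Arm A difference in change from Day 1 to Day 22 in the ablation-zone CD8+/CD4+ ratio. Report it with a two-sided 95% confidence interval and label it an unpowered pilot estimate. Replace the wording in Section 3.1 that promises a determination with wording that promises an estimate. Keep the within-arm changes as supportive results. A log scale or baseline adjustment is optional.

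**(b) Keep the analysis and change the question.** Reword the objective and hypothesis in Section 3.1 to within-arm estimation: change after HIFU alone (Arm A) and change after pembrolizumab plus HIFU (Arm B). Make no claim about the effect of adding pembrolizumab, and bring Sections 4.4 and 4.4.1 into line.

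**Cost.** Both options are wording changes. Option (a) adds one analysis of data already being collected; its price is a wide interval, so it yields an estimate and not a determination. Neither option needs extra patients or biopsies.

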### 3.2 Secondary Objectives & Hypotheses

**Objective:** To assess the adverse event profile of pembrolizumab and HIFU

**Hypothesis:** The combination of pembrolizumab and HIFU will result in adverse event profiles similar to previously reported profiles for each modality given alone.

**Product:** Pembrolizumab

**Protocol/Amendment No.:** UVA Breast 48

V04-13-21

### 3.3 Exploratory Objectives

- (1) **Objective:** To compare CD8+ T-cell responses at peri-ablation zones when pembrolizumab is given before or after HIFU. (CD8+/CD4+ ratios compared between arms)
- (2) **Objective:** To evaluate clinical responses at local and distant metastatic sites by CT scan as measured by RECIST 1.1.
- (3) **Objective:** To estimate the progression free survival (PFS) of breast cancer subjects treated with HIFU in combination with pembrolizumab.
- (4) **Objective:** To estimate the overall survival (OS) of subjects with breast cancer treated with HIFU in combination with pembrolizumab.
- (5) **Objective:** To evaluate immune responses to HIFU plus pembrolizumab by flow cytometric, immunohistochemical, cytokine, or other methods.

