### 5.2.3 Timing of Dose Administration

Trial treatment should be administered on Day 1 of each cycle after all procedures/assessments have been completed as detailed on the Trial Flow Chart ([Section 6.0](#)). Trial treatment may be administered up to 3 days before or after the scheduled Day 1 of each cycle due to administrative reasons.

All trial treatments will be administered on an outpatient basis.

**Product:** Pembrolizumab

**Protocol/Amendment No.:** UVA Breast 48

V04-13-21

Pembrolizumab 200 mg will be administered as a 30 minute IV infusion every 3 weeks. Staff should make every effort to target infusion timing to be as close to 30 minutes as possible. However, given the variability of infusion pumps, a window of -5 minutes and +10 minutes is permitted (i.e., infusion time is 30 minutes: -5 min/+10 min).

The commercial Pembrolizumab product provided by Merck will be prepared and administered per standard practice.

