#### **7.1.2.8 Tumor Tissue Collection and Correlative Studies Blood Sampling**

##### **7.1.2.8.1 Core Biopsies**

Tumor tissue biopsies will occur at baseline and at cycle 2 as per Flow Chart 6.1 above. Optional tumor biopsies are permitted at cycle 4 where deemed safe. For the core biopsies, 14-18 gauge needles may be used for tissue sampling. Ultrasound guidance or CT guidance may be used at the time of the biopsy. The tissue specimens will be collected in the following priority:

- (1) Formalin-fixed for paraffin embedding (TMA for IHC and TCR sequencing)
- (1) RPMI for single cell suspensions (flow cytometric analyses)
- (1) Trizol for RNA extraction (gene expression analyses)

Leftover samples may be banked and stored for future biomedical research

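### Exploratory objective 3.3(1) compares pembrolizumab before versus after HIFU, but at the Day 22 biopsy, the only mandatory post-HIFU sample, Arm A has had no pembrolizumab, so that tissue carries no information on sequence

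*Combined protocol and SAP*

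**What the plan says.** Section 3.3, objective (1), sets out to compare CD8+ "T-cell responses at peri-ablation zones when pembrolizumab is given before or after HIFU". A parenthesis adds that CD8+/CD4+ ratios are compared between arms. No biopsy day is given.

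The schedule is in Section 2.1 and agrees with Table 3 and the flow charts in 6.1:

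- HIFU: "Subjects on both arms will undergo HIFU treatment on day 15".
- Arm A: "Subjects randomized to Arm A will receive pembrolizumab administered IV every 3 weeks on days 22, 43, and 64".
- Arm B: "Subjects randomized to Arm B will receive pembrolizumab administered IV every 3 weeks on days 1, 22, 43 and 64".
- Mandatory tissue: "Biopsies of tumors treated with HIFU will be completed on all patients at days 1 and 22".
- Later tissue, from Section 7.1.2.8.1: "Optional tumor biopsies are permitted at cycle 4 where deemed safe". Cycle 4 starts on Day 64.

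Section 5.2.3 fixes the order on a dosing day: "Trial treatment should be administered on Day 1 of each cycle after all procedures/assessments have been completed".

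Footnote m to the flow charts divides the cycle 2 biopsy between the central ablated zone and the peri-ablation zone, three passes each. Footnote k, which covers the optional cycle 4 biopsies, names no zone.

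Section 2.1 labels Days 15 to 21 as HIFU alone in Arm A and as the combination in Arm B. Section 8.2 estimates the change in TILs from baseline to 3 weeks within each arm, and the peri-ablation CD8+ change by arm.

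**The concern.** Objective 3.3(1) asks about the order of two treatments. To answer it, both arms must have received both treatments before the tissue is taken. At Day 22 only Arm B has. A between-arm difference there shows what one dose of pembrolizumab adds to HIFU, which is the question of the primary objective in 3.1 asked of a neighbouring zone.

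The risk is mislabelling. A Day 22 difference reported under the heading of before versus after could be taken as evidence about sequence, when it compares drug with no drug. Section 8.1 says the pilot should inform the design of a larger trial of combined therapies, so the label on the contrast matters even though the objective is exploratory. More participants would not help, because the problem is what the contrast estimates and not its precision.

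**Working it through.** **Inputs.** HIFU on Day 15 in both arms; Arm A doses on Days 22, 43 and 64; Arm B doses on Days 1, 22, 43 and 64 (2.1, Table 3). Biopsies on Day 1, Day 22 and, optionally, Day 64 (2.1, 7.1.2.8.1). Cycles are 21 days (6.1, footnote a), so cycle 2 starts on Day 1 + 21 = 22 and cycle 4 on Day 1 + 63 = 64. On these days procedures come before the infusion (5.2.3).

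**The plan's own figure.** Section 8.2 gives 80% power at an effect size of 1.44 with n = 6 for the within-arm change. A paired t-test at two-sided 0.05 (an assumption, as the level is not stated) gives 80.3%, so the figure reproduces. It concerns change within an arm, and the present point does not depend on it.

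**Dose count.** Doses before a biopsy on day d = number of scheduled dosing days earlier than d.

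| Biopsy | Arm A, before HIFU | Arm A, after HIFU | Arm A, total | Arm B, before HIFU | Arm B, after HIFU | Arm B, total |
|---|---|---|---|---|---|---|
| Day 22 (mandatory) | 0 | 0 | 0 | 1 (Day 1) | 0 | 1 |
| Day 64 (optional) | 0 | 2 (Days 22, 43) | 2 | 1 (Day 1) | 2 (Days 22, 43) | 3 |

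**Time since first dose at Day 64.** Arm A: 64 − 22 = 42 days. Arm B: 64 − 1 = 63 days.

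**Reading the table.** At Day 22 no Arm A participant has had pembrolizumab after HIFU, so the after condition does not yet exist. At Day 64 both arms have the same two scheduled post-HIFU doses, and the whole scheduled difference is Arm B's Day 1 dose. Order has not been swapped; a pre-HIFU dose has been added.

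**Visit windows.** The ±3-day windows do not change this, because 5.2.3 puts the dose after the day's procedures. If a biopsy did slip past the infusion, the Arm A participant would have at most a few days of exposure.

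**Precision at Day 64, for scale.** This uses a two-sample t-test at two-sided 0.05 (assumed). If all 6 per arm gave a usable sample, 80% power would need an effect size of 1.80, and power at 1.44 would be 61%. With 3 per arm, an assumed uptake, these become 3.07 and 27%. The documents give no expected uptake.

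**The case against.** The strongest reply is that before and after are simply the arm labels in the Trial Summary (Section 1.0), so 3.3(1) means no more than comparing Arm A with Arm B. Section 2.1 already tells the reader that Arm A is HIFU alone in Days 15 to 21. The objective is exploratory, Section 8.1 says the trial is not powered across arms, and Section 8.2 disclaims definitive comparisons and plans only estimates by arm. It is also true that 3.3(1) names no day, so Day 22 is not stated to be its time point.

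Much of this stands. It makes harm remote, and it means the plan cannot be said to have assigned the sequence question to Day 22. It does not cure the wording. The labels describe the whole regimen, while the mandatory tissue covers only its first three weeks, and disclaimers about power do not change what a contrast estimates.

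Two stronger readings are tempting. A reader might infer that the Day 64 comparison is invalid because sequence is confounded with exposure. The schedule does not support that in general: Arm B's extra dose is the before strategy itself, so for starting before against starting after, the third dose and the longer time on drug belong to what is compared. They confound only the narrower question of order at equal exposure. The more general weakness at Day 64 is that the biopsy is optional. A reader might also infer that a Day 22 difference would fix the sequence in a later trial. Nothing in 8.1 or 8.2 plans that.

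**Conclusion.** The point holds as a mismatch between an objective and the tissue available for it. The mandatory post-HIFU biopsy compares 1 dose with 0, so it bears on adding pembrolizumab to HIFU and not on sequence. The optional Day 64 biopsy compares 3 doses with 2, and 63 with 42 days since first dose. It can describe two whole strategies in those who agree to the biopsy, but not order at equal exposure. Because peri-ablation passes are specified only for cycle 2, Day 64 samples may contain no peri-ablation tissue at all.

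This rests on doses and biopsies being given as scheduled and in the order set by 5.2.3. It should be corrected because it changes what may be concluded. The exploratory, unpowered status limits the likely consequence.

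**What to change.** 1. Reword 3.3(1), and the matching peri-ablation text in 8.2, so that the Day 22 comparison is HIFU plus pembrolizumab (Arm B) against HIFU alone (Arm A), with an explicit statement that no conclusion on sequence follows.
2. Limit any before/after statement to a descriptive report of the optional Day 64 samples. Give dose count and days since first dose for each participant, and note the self-selection and Arm B's additional pre-HIFU dose.
3. Add to footnote k and Section 7.1.2.8.1 that the zone sampled in an optional biopsy of the HIFU-treated lesion is recorded. Include only samples documented as peri-ablation. If this cannot be done, drop the before/after objective.
4. In the same edit, reconcile the status of peri-ablation CD8+ response, which is exploratory in 3.3 and secondary in 8.1.

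The cost is wording in 3.3, 8.1, 8.2, footnote k and 7.1.2.8.1, plus one recorded item per optional biopsy. No dose, visit or mandatory sample changes. The price is that the sequence objective becomes a description in a self-selected subset or disappears.
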